Chronic effects of deep brain stimulation on cortical local field potentials in Parkinson's disease and primary dystonia Study

(Activa PC+S)

NCT Number: NCT01934296

Document Date: September 14, 2017

Protocol Synopsis

| Title | Chronic effects of deep brain stimulation on cortical local field potentials in Parkinson's disease and primary dystonia |
|-----------------|--|
| Study Phase | Phase I |
| Device(s) | Device Information: Devices to be used in this study are grouped below according to FDA approval. All are Medtronic Devices. Investigational |
| | Activa PC+S implantable pulse generator, Model 37604 Sensing Programmer Model 8181 for Activa PC+S Sensing Programmer Software Model 8180 for Activa PC+S Lead extension Model 37087 Nexus-D System Nexus-D Application Programming Interface (API) |
| | Intercept Patient Programmer, model 37441Approved for other indications Medtronic Lead Model 3391 Medtronic Resume II paddle electrode model 3587A |
| | Approved for the intended indication |
| | N'Vision Clinical Programmer Model 8840 Clinician Programmer Software Model 8870 Patient Programmer Model 37642 Lead Model 3389 External Neurostimulator 37022 Lead extension model 37086 Activa SC 37603 single channel pulse generator |
| Indication | Adults with Parkinson's disease (PD) or primary generalized or segmental dystonia, who experience inadequate symptom relief in the setting of optimal medical therapy by a movement disorders neurologist, and who have been offered implantation of a deep brain stimulator system. |
| Sponsor Contact | [name]., MD Professor of Neurological Surgery University of California, San Francisco [name] [contact] [contact] |

| | [contact] |
|----------------|--|
| Medical Safety | The medical safety monitor board (MSMB) consists of a neurologist and |
| Monitor | neurosurgeon outside of our home institution, who have no direct involvement |
| | in this study but who have expertise in implantable devices. The neurologist is |
| | [name] at the University of Florida, Gainesville, and the neurosurgeon |
| | is [name] at the University of Washington, Seattle. Treatment |
| | related adverse events assessed as definitely, probably, or possibly related to |
| | study procedures and either serious or unexpected, noted by any study |
| | personnel will be reported within 10 working days of their knowledge of the |
| | event to the MSMB. The MSMB will then advise the PI on potential changes in |
| | procedures to improve safety, or, in the event of multiple serious adverse |
| | |
| | events, may invoke stopping rules. |
| Treatment | Long-term stimulation of the basal ganglia for Parkinson's disease or primary |
| | dystonia |
| Study Site | University of California, San Francisco |
| | [name] |
| | [name] |
| Study Design | This is a single-center study of the neurophysiology of human movement |
| | disorders with two goals: 1) Assess the feasibility of chronic brain recording |
| | using a novel fully implantable pulse generator (Medtronic Activa PC+S), which |
| | has the capability of sensing and storing local field potentials (LFPs) recorded from implanted electrodes, in addition to providing therapeutic deep brain |
| | stimulation (DBS). 2) Study acute and chronic effects of therapeutic DBS on |
| | cortical LFPs. Participants will also have the opportunity to participate in an |
| | add-on study to test practical applications of this device, such as "closed loop" |
| | stimulation, in which neural feedback is used to program optimal DBS settings. |
| | These additional studies will utilize the Nexus-D (Medtronic), which streams |
| | data noninvasively from Activa PC+S to an external computer in near real time. |
| | Study subjects will have implanted, in addition to their standard DBS |
| | electrode(s), a unilateral flexible 4-contact electrode (Medtronic 3391 lead or |
| | 3587A lead). This lead will be advanced through the same burr hole used for |
| | the DBS lead implants. This electrode array does not penetrate the brain |
| | surface, but rests on the surface of the motor cortex. The cortical electrode, as |
| | well as the standard therapeutic DBS electrode implanted on that side, will be |
| | attached to a Medtronic Activa PC+S pulse generator placed in the ipsilateral |
| | pectoral area. On the contralateral side, for patients scheduled for bilateral DBS |
| | implantation, a standard therapeutic DBS electrode will be connected to a |
| | standard Medtronic single channel pulse generator (Activa SC). At multiple |
| | time points up to 24 months post implantation, subjects will have outpatient |
| | visits to collect data, download cortical LFPs, and, in the add-on Nexus-D study, |
| | test applications of closed loop DBS. Some subjects who have signed consent |
| | for the Nexus-D2 substudy will have the option for data downloading and |
| | Tor the Nexus-D2 substudy will have the option for data dowinioading and |

| | operant conditioning at home. The goal of the operant conditioning is to |
|--------------------|--|
| | evaluate whether PD patient practice in modulating brain activity may lead to |
| | clinical improvement of PD symptoms |
| | |
| Objectives | In fifteen patients undergoing DBS implantation for PD or primary dystonia (10 PD; 5 dystonia), we will implant a unilateral subdural cortical electrode in addition to the DBS electrode, and connect these to a novel implantable pulse generator that can store field potential data (Medtronic Activa PC+S). At multiple time points post-implantation in our clinic, we will record and download cortical and basal ganglia LFPs on and off of DBS therapy in the following behavioral conditions: a.) rest b.) during a computer controlled binary choice arm reaching task c.) walking up and down a hallway Hypotheses: Long term recording of cortical LFPS is technically feasible with stable signals over 1 year, without adverse events 2) Chronic (6 and 12 months) basal ganglia DBS alters the spectral characteristics of the M1 LFP (spectral power in beta and gamma bands), the magnitude of movement related M1 beta band change, and the coupling between beta rhythms and broadband gamma activity. We expect that in PD, DBS-induced changes will appear in early recordings |
| | (immediately after starting DBS), whereas in primary dystonia, cortical |
| | changes will be seen only after long-term DBS. |
| | 3) DBS-induced changes in abnormal cortical oscillatory activity may predict the degree of DBS-induced improvement in motor function |
| | Markers of abnormal cortical or basal ganglia oscillatory activity can help determine clinically effective stimulation settings. |
| Patient Population | Study subjects will be adults with Parkinson's disease (PD) or primary dystonia, recruited from a clinic population of patients scheduled to undergo unilateral or bilateral DBS implantation for amelioration of their movement disorder symptoms. |
| Sample Size | 15 subjects |
| Efficacy | Clinical rating scales of motor function: |
| Assessments | For PD patients: Unified Parkinson's Disease Rating Scale (UPDRS) parts I-IV and |
| | dyskinesia rating scales. UPDRS part III will be scored on and off of |
| | antiparkinsonian medications. For dystonia patients: Burke-Fahn Marsden |
| | Dystonia Rating Scale (BFMDRS) and Toronto Western Spasmodic Torticollis |
| | rating scale (TWSTRS). |
| | Other rating scales (all patients): Clinician Global Impression of Change (CGI-C) |
| C . (.) | and Patient Global Impression of Change (PGI-C). |
| Safety | 1)Physical examination at all study visits |
| Assessments | 2) Check of pulse generator stimulation parameters, impedance measurements, |
| | and battery voltage at all study visits |
| | 3) Surgical or nonsurgical protocol-defined adverse events as recorded on |
| | adverse events case report forms4) Assessment of suicidality using the Columbia Suicide Severity Rating Scale, at |
| | all protocol-defined outpatient visits |
| | |

| 5) In visits where the Nexus will be used for closed loop stimulation, all possible |
|---|
| stimulation settings are preselected by clinicians to avoid the possibility of |
| producing major stimulation-induced adverse effects |

Statistical Methods and Data Analysis

ECoG and LFP data will be analyzed in the frequency domain for mean log power in the beta and gamma bands, movement related changes in beta and gamma band power, and coupling between low frequency rhythms and broadband gamma power (12, 20, 21). Using a repeated measures ANOVA statistical analysis, summary statistics for power in relevant frequency bands, movement related power changes, and indices of phase-amplitude coupling will be compared at different time points, different DBS conditions (on and off), and different disease states (PD or primary dystonia).

Although the sample size is small, in each disease group we will assess the correlation between these brain physiology measures, and clinical instruments used to measure the motor benefit produced by DBS. In particular we will ask: 1) Did the degree of cortical synchronization, as assessed by a quantitative index of phase-amplitude coupling (PAC) prior to starting stimulation therapy, correlate with the degree of benefit produced by DBS (difference between clinical ratings at 12 months on stimulation and baseline pre-implantation, off medication). 2) Did the magnitude of DBS-induced suppression of cortical synchronization (difference between PAC on-stimulation at 12 months, versus prior to starting stimulation therapy) correlate with the degree of benefit produced by DBS (difference between PAC on-stimulation, off medication) 3) For the add-on study examining potential therapeutic uses of Activa PC+S: 1) Did the DBS stimulation settings which minimized metrics of cortical synchronization or basal ganglia synchronization, produce a therapeutic benefit compared with the off stimulation and off medication state; and 2) Did operant control of cortical or basal ganglia rhythms produce a therapeutic benefit compared with the off stimulation and off medication state; and off medication state prior to learning operant control.

Since this is a pilot study of chronic cortical recording, the sample size is likely to be too small to provide definitive answers to all research questions. Based on this exploratory analysis, it is anticipated that the next phase of the study will focus on a subset of the research aims, with 10-15 subjects per group.

Sample size calculation: This is a pilot study of a novel chronic brain recording technique. The goals are to assess technique feasibility, to collect pilot data that will be used to frame more detailed hypothesis about DBS mechanisms, and (in the add-on study using Nexus-D) to explore potential strategies for therapeutic use of the Activa PC+S neural interface. Thus, there is no formal sample size calculation.

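### The board may stop the study for multiple serious adverse events, but the only reporting route described sends it events already judged at least possibly related

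*Combined protocol and SAP*

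**What the plan says.** The Medical Safety Monitor row of the Protocol Synopsis sets up a two-person board, a neurologist and a "neurosurgeon outside of our home institution, who have no direct involvement" in the study. It then gives the reporting rule and the board's powers.

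- **What is reported.** The rule covers treatment "related adverse events assessed as definitely, probably, or possibly related to" "study procedures and either serious or unexpected, noted by any study" personnel. An event must therefore pass the relatedness test and must also be serious or unexpected.
- **How fast.** Such events noted by study "personnel will be reported within 10 working days of their knowledge of the" event.
- **What the board may do.** It then advises the principal investigator on changes in "procedures to improve safety, or, in the event of multiple serious adverse" "events, may invoke stopping rules". This clause has no relatedness limit and no number, and the stopping rules themselves are not set out.

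The Safety Assessments row separately lists "3) Surgical or nonsurgical protocol-defined adverse events as recorded on" case report forms. It states no relatedness limit, and it does not say that the forms, or a listing of all serious events, go to the board. No periodic board review is described.

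**The concern.** The reporting rule and the stopping clause describe different sets of events. The first is restricted by attribution. The second, as worded, is not. If the clause means all serious events, the board has no described means of counting them.

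Attribution is hard to make in this design. According to the Study Design row, the cortical research lead goes through the burr hole used for the DBS lead, and on that side both leads connect to the investigational generator. A serious event there could be put down to the standard operation or to the added hardware. No control group is described that would help to separate the two. The text also does not say whether the standard DBS implant counts as a study procedure.

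What is at stake is the board's independent view. Two outside specialists in implantable devices are well placed to question an attribution, or to notice that several serious events called unrelated look alike. Under the rule as written they need not be told of such events.

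**Working it through.** **Comparing the two provisions.** All entries come from the Medical Safety Monitor row.

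| Feature | Reporting rule | Stopping clause |
|---|---|---|
| Relatedness | Definitely, probably or possibly related to study procedures | Not stated |
| Seriousness | Serious or unexpected | Serious |
| Number | Each event | Multiple, undefined |
| Who attributes | Not named | Not applicable |

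The clause can be read in two ways.

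1. It counts all serious adverse events. The described route then delivers only part of that set.
2. It counts serious events among those already reported. Rule and clause then agree, but the count still depends on attribution made upstream.

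The board's information is filtered by attribution under both readings. Only the first also makes the two provisions inconsistent.

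**Who attributes.** The text does not say. Events are noted by study personnel and have already been assessed when the external board receives them, so assessment by study personnel is a reasonable inference, though not a stated fact.

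**Possible size.** There is no plan figure to reproduce. The plan gives no serious-event rate and no numerical trigger, and under Sample size calculation it says "Thus, there is no formal sample size calculation". The one document input is n = 15 (Sample Size row; 10 PD + 5 dystonia). The rates below are assumptions.

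*Expected subjects with a serious event judged unrelated* = n × u, where u is the assumed proportion of subjects:

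- u = 0.05: 15 × 0.05 = 0.75
- u = 0.30: 15 × 0.30 = 4.5

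These are subjects. They equal extra reports only if each such subject has one event.

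*Chance that the board hears of serious events in at least 2 subjects.* Let p be the assumed chance that a subject has a serious event, s the assumed share judged at least possibly related, and q = p × s. With subjects independent, and multiple taken to mean 2 or more subjects (also an assumption):

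P = 1 − (1 − q)^15 − 15q(1 − q)^14

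For example, p = 0.20 and s = 0.50 give q = 0.10, so P = 1 − 0.206 − 0.343 = 0.451.

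| p | s = 1 (all sent) | s = 0.75 | s = 0.50 | s = 0.25 |
|---|---|---|---|---|
| 0.10 | 0.451 | 0.312 | 0.171 | 0.053 |
| 0.20 | 0.833 | 0.681 | 0.451 | 0.171 |
| 0.30 | 0.965 | 0.883 | 0.681 | 0.312 |

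The first column also shows the position if every serious event were sent. If every serious event is judged at least possibly related, s = 1 and nothing is lost. The table shows what the board would see. It says nothing about whether the board would stop the study.

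**The case against.** The strongest reply is that there is no mismatch. The board acts after receiving reports, and the stopping clause follows in the same sentence, so multiple serious events naturally means multiple reported ones. That reading is available, and the documents cannot be said to contradict themselves outright. It does not remove the dependence on prior attribution.

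The second reply is that the filter is loose. It admits possibly related events noted by any study personnel. With a shared burr hole and generator, few surgical or hardware events on that side could be ruled out even as possibly related. The rule also opens with treatment-related events, and the Treatment row defines treatment as long-term basal ganglia stimulation. A reader might infer that anything put down to standard DBS never reaches the board, but the text does not settle that. This reply stands, and it is why the loss may be small.

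The third reply is that the available text is a synopsis. It mentions stopping rules and protocol-defined events without setting them out, so a fuller reporting route may exist elsewhere. That also stands. The point is that no other route is described here.

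**Conclusion.** The concern holds in limited form. The only described route to the board is filtered by relatedness and the stopping clause states no such filter, so the set of events that the clause counts is unclear. On either reading the board depends on attribution made before it is informed.

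The size cannot be established from the documents. Under the assumed 5% to 30%, serious events in about 0.75 to 4.5 of 15 subjects would go unreported to the board. The true figure could be zero.

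Two stronger conclusions are tempting and are not supported:

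- A reader might infer that the first hypothesis, on feasibility without adverse events, rests on attribution that nobody reviews. Neither that hypothesis nor the case report forms carry a relatedness limit, and nothing says that the board's reporting filter governs the data used to judge it.
- A reader might infer that attribution is the whole of the safety judgement. The Safety Assessments row also lists physical examination, stimulation parameters, impedance, battery voltage and a suicidality scale, and none is described as depending on attribution.

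This is a worthwhile, inexpensive improvement to oversight. It does not show that a safety signal would be missed.

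**What to change.** Amend the reporting rule in the Medical Safety Monitor row in three respects:

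1. Send the board every serious adverse event, with the attribution and the role of the person who made it, within the existing 10 working days.
2. Keep the relatedness filter for events that are unexpected but not serious.
3. Reconcile the reporting rule and the stopping clause so that both refer to the same set of events.

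This changes what is reported and proposes no stopping threshold. It also does not define multiple, which the plan leaves open.

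The cost is a short text change and a few more reports: about 0.75 to 4.5 over the study under the assumed rates with one event per affected subject, and more if subjects have several. No new procedure is needed.

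If the sponsor keeps the present filter, the text should at least say whether the stopping clause counts only related events and who decides relatedness.

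### Does hypothesis 1 need its own signal-stability measure and event list before the feasibility and coupling results can be read?

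*Combined protocol and SAP*

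**What the plan says.** In the Synopsis, Objectives, hypothesis 1 is "Long term recording of cortical LFPS is technically feasible with stable signals over 1 year, without adverse events". No metric, threshold or list of events follows it.

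Hypothesis 2, in the same section, is that "Chronic (6 and 12 months) basal ganglia DBS alters the spectral characteristics of the M1 LFP", with movement-related beta change and beta-gamma coupling as further outcomes. In PD the change is expected early. In dystonia "changes will be seen only after long-term DBS".

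Statistical Methods and Data Analysis names log beta and gamma power, movement-related power change and coupling. By repeated measures ANOVA these "will be compared at different time points, different DBS conditions (on and off), and different disease states (PD or primary dystonia"). Question 2 there asks: "Did the magnitude of DBS-induced suppression of cortical synchronization (difference between PAC on-stimulation at 12 months, versus prior to starting stimulation therapy"), and whether that difference correlates with clinical benefit. On later use of the results it says: "Based on this exploratory analysis, it is anticipated that the next phase of the study will focus on a subset of the research aims".

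Safety Assessments lists "Check of pulse generator stimulation parameters, impedance measurements" and battery voltage at all study visits. It also lists "Surgical or nonsurgical protocol-defined adverse events as recorded on" case report forms. The Medical Safety Monitor entry has a relatedness grading, used there for reporting to the safety board.

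**The concern.** Feasibility is the first of the two goals under Study Design, yet the only signal measures planned for comparison over time should stay stable under hypothesis 1 and change under hypothesis 2.

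- **Question 2.** The coupling difference runs from before stimulation to 12 months on stimulation, so stimulation state and elapsed time change together. A worsening signal-to-noise ratio lowers a normalised coupling index, which is the direction labelled as suppression.
- **Dystonia.** Change that appears only late is also the time course of slow signal loss. A chronic effect that persists off stimulation would show in both recordings, as drift does.
- **Safety clause.** Read literally, one adverse event of any kind refutes hypothesis 1, although every subject also receives standard DBS.

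At stake is the choice of aims for the next phase: a fall in coupling that was really signal loss could be carried forward as an effect of stimulation, or standard DBS events could be held against cortical recording.

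**Working it through.** **Plan's own figure.** 10 PD + 5 dystonia = 15, as stated. There is no alpha, power or effect size to reproduce.

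**Can signal loss look like coupling suppression?** The documents give no index formula, so the model is assumed: gamma amplitude 1 + 0.3·cos(phase), independent noise with power *r* times gamma signal power, mean amplitude by phase proportional to √(signal power + noise power), and an 18-bin Kullback-Leibler modulation index. A 20% amplitude loss at constant noise takes *r* to *r*/0.8² = *r*/0.64. For shallow modulation the index ratio, after over before, is ((1+*r*)/(1+*r*/0.64))².

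| *r* | Shallow-modulation formula | Modulation index ratio | Normalised mean vector length ratio |
|---|---|---|---|
| 0 | 1.000 | 1.000 | 1.000 |
| 0.1 | (1.1/1.15625)² = 0.905 | 0.897 | 0.948 |
| 0.5 | (1.5/1.78125)² = 0.709 | 0.700 | 0.837 |
| 1.0 | (2/2.5625)² = 0.609 | 0.604 | 0.777 |

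So the index falls by 0% to 40% (0% to 22% for mean vector length) with coupling unchanged. The effect is possible, and its size depends on a noise level the documents do not give.

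**What do the planned comparisons already separate?** If amplitude is multiplied by *g*, log10 power shifts by 2·log10(*g*): −0.194 for *g* = 0.8. Within a visit the shift is the same on and off stimulation, so it cancels from the on/off difference. It cancels likewise from a movement-related change expressed in log power. With appreciable noise the cancellation is only approximate. For coupling, off-stimulation recordings at the same visits let 12-month on and off values be set side by side. The disease comparison is a weak check: the 95% half-width for a PD-minus-dystonia difference in change is 2.160 × √(1/10 + 1/5) = 1.18 SD.

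**What would drift do to question 2?** That question correlates the coupling difference with clinical benefit. Drift unrelated to benefit adds noise to one variable and pulls the correlation towards zero.

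**Safety clause, literal reading.** If each subject has probability *p* (assumed) of a counted event from standard DBS alone, the clause holds in all 15 with probability (1−*p*)^15: 0.9^15 = 21%, 0.8^15 = 3.5%, 0.7^15 = 0.5%. These figures need both the assumed rates and a reading in which standard DBS events count, which the text does not state.

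**Would a preset usability threshold help?** A natural candidate is gamma signal power at least 10 times the noise floor at 12 months. Gamma power is itself a hypothesis 2 outcome: a subject at 12:1 whose gamma power truly falls 20% has 12 × 0.8 = 9.6:1 and would be scored a feasibility failure. Nor does one visit show stability. A fall from 100:1 to 10:1 is an amplitude loss of 1 − √0.1 = 68%; it still passes, with the modulation index at 0.827 of its start (down 17%). A recording that reaches 10:1 after a 20% loss has a ratio of 0.929 (down 7%). The threshold therefore repeats the overlap with hypothesis 2 and does not bound the drift.

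**The case for a change.** The strongest case for a change is that feasibility is the leading goal and should not depend on definitions chosen after the data are seen. Impedance is listed only as a safety check, with no criterion and no statement of which contacts it covers, and it does not itself measure LFP quality. The question 2 difference contains no 12-month off-stimulation term. The relatedness grading is a reporting rule and is not linked to hypothesis 1. A short clarification would cost little.

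Most of this is factually right. The missing definitions are real, and a late fall in coupling taken alone would be ambiguous. What does not follow is that a planned analysis gives a wrong result. The cortical lead is connected to the sensing generator (Study Design), so impedance and circuit integrity can be tabulated for its contacts if the visit check includes them. The off-stimulation recordings needed to interpret the coupling difference are already planned. Hypothesis 1 is about long-term cortical recording, so counting events related to that recording, with others listed separately, is its natural reading. Surgical events will still need judgement because the two leads share a burr hole. The text supplied is a synopsis that refers to protocol-defined events, so a fuller list may exist elsewhere.

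**Conclusion.** No change to the plan is needed. The synopsis leaves two definitions unwritten: what stable means, and which events count. An analyst can fill both sensibly from data the plan already collects, and doing so alters no planned comparison.

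The possible distortion is a 0% to 40% fall in a modulation index for a 20% amplitude loss. That range rests on an assumed index, modulation depth, amplitude loss and noise level. The low probabilities for the safety clause rest on assumed event rates and a literal reading.

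Impedance can flag drift but cannot correct it, and a gamma-based threshold would bring back the overlap it was meant to remove, so more prespecification would gain little. With 15 subjects, even 0/15 related events leaves an exact two-sided 95% upper limit of 1 − 0.025^(1/15) = 21.8%. The plan already calls itself a pilot, likely too small for definitive answers, and no error rate or decision rule depends on these definitions. A late fall in coupling should still be read beside the off-stimulation and impedance data; that is a matter of interpretation.

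### Cheap improvement: a repeated measures ANOVA in its classical form would drop any of the 10 PD or 5 dystonia subjects with a missing recording; a mixed model would keep the rest of their data

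*Combined protocol and SAP*

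**What the plan says.** The Statistical Methods and Data Analysis section of the synopsis names one method for all the physiology measures: "Using a repeated measures ANOVA statistical analysis, summary statistics for power in relevant frequency bands", movement-related power change and phase-amplitude coupling (PAC) are compared across time points, "different DBS conditions (on and off), and different disease states (PD or primary dystonia"). It does not say which form of the ANOVA is meant, which time points enter, or how a subject with a missing recording is handled.

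The Objectives row gives 10 PD and 5 dystonia subjects and says that at each of several clinic visits "we will record and download cortical and basal ganglia LFPs on and off of DBS therapy". Its first hypothesis is "Long term recording of cortical LFPS is technically feasible with stable signals over 1 year". The Study Design row has "time points up to 24 months post implantation, subjects will have outpatient" visits. The study is described as an exploratory pilot with no formal sample size calculation, and its results are expected to narrow the aims of the next phase.

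**The concern.** A classical repeated measures ANOVA needs a value in every time-by-DBS cell for each subject. A subject who lacks one cell leaves the whole analysis, including comparisons for which that subject's data are complete. Each dystonia subject is a fifth of that group.

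Missing recordings are plausible because the study is partly a test of whether an investigational implant can deliver them. An analysis that keeps everyone only if the feasibility hypothesis succeeds in full is a poor match for a feasibility study. What is at stake is precision in the estimates that will guide the choice of later aims.

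**Working it through.** The plan states no power, standard error or missing rate, so there is no figure of its own to reproduce.

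**Inputs from the documents.** 10 PD and 5 dystonia subjects; recordings on and off DBS; 6 and 12 months as the chronic time points (Objectives, hypothesis 2).

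**Assumptions.** Three time points (early, 6 and 12 months), hence 3 × 2 = 6 cells per subject; 5% or 10% missing; three patterns of loss, namely single cells independently, whole visits independently, or permanent loss with that chance at each visit. Residual variance is 1, under three variance structures: (a) subject intercept 1; (b) intercept 1, subject-by-visit 0.5, subject-by-DBS 0.5; (c) as (b), plus subject-specific drift in the DBS effect.

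**Step 1: complete subjects.** The complete fraction is (1 − m)^k, with k = 3 visits or 6 cells.

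| Loss | m | Fraction | PD of 10 | Dystonia of 5 | P(2 or fewer dystonia complete) |
|---|---|---|---|---|---|
| Visits | 5% | 0.95³ = 0.857 | 8.6 | 4.3 | 0.023 |
| Visits | 10% | 0.90³ = 0.729 | 7.3 | 3.6 | 0.127 |
| Cells | 5% | 0.95⁶ = 0.735 | 7.4 | 3.7 | 0.120 |
| Cells | 10% | 0.90⁶ = 0.531 | 5.3 | 2.7 | 0.441 |

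**Step 2: precision.** The quantity is the standard error from complete subjects divided by the standard error from all available recordings, for the PD-versus-dystonia difference in early-to-12-month change. It uses generalised least squares with known variances, 2,500 simulated data sets per scenario, keeping runs with at least 2 complete subjects per group. Ranges cover the three structures and two outcomes: the on-minus-off difference, and the on-stimulation value taken as change from before stimulation.

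| Loss | 5% | 10% |
|---|---|---|
| Permanent | 1.016–1.031 | 1.031–1.058 |
| Whole visits | 1.049–1.064 | 1.103–1.128 |
| Single cells | 1.133–1.154 | 1.249–1.289 |

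The number of time points matters. With only the early and 12-month visits in the model, the rise is 1–3% (visits or permanent loss) and 6–9% (cells) at 5%, and 2–6% and 13–17% at 10%. With five time points, as might be needed to reach 24 months, it is 8–12% and 25–28% at 5%, and 15–24% and 43–47% at 10%.

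**Step 3: fitted model.** This was a REML fit with subject, subject-by-visit and subject-by-DBS effects and Satterthwaite degrees of freedom, 2,000 runs per scenario. Mean 95% CI half-widths for the on–off contrast without drift, complete-case over mixed model, are:
- 5% missing: 2.472/2.311 = 1.07 (visits) and 2.714/2.336 = 1.16 (cells)
- 10% missing: 2.719/2.391 = 1.14 (visits) and 3.263/2.448 = 1.33 (cells)

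Type I error for the same contrast at a nominal 5%:

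| Method | No drift | Subject-specific drift |
|---|---|---|
| Mixed model | 4.7–6.0% | 8.1–9.9% |
| Complete-case ANOVA | 4.2–5.8% | 8.2–9.3% |

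The per-subject contrast t test gave 3.8–5.6% overall. A random intercept alone is not safe: with complete data and six assumed structures, its type I error ran from 0.3% to 18%.

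**Step 4: what the contrast can show.** With complete data the per-subject t test has 10 + 5 − 2 = 13 df. The 95% half-width is t(0.975, 13) × √(1/10 + 1/5) = 2.160 × 0.548 = 1.18 SD, where SD is the between-subject SD of the contrast. Power is 39% at 1.0 SD and reaches 80% at 1.66 SD.

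**Step 5: can the full factorial be fitted?** The PAC comparison uses a recording made before stimulation starts, which appears to have no on-DBS cell. Pre-stimulation plus three visits, two states and two diseases make 4 × 2 × 2 = 16 parameters but only 16 − 2 = 14 observed cells. The design matrix has rank 14, so the full factorial is not estimable with that recording included.

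**The case against.** The strongest reply is that the fault is conditional. A reader might infer that the plan will discard incomplete subjects, but the documents do not say so. An ANOVA in long format with subject as a factor need not drop whole subjects, and the text is a synopsis. This stands, and it limits the point to the classical form. It does not remove it, because nothing in the text rules that form out.

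Second, on and off recordings come from the same visits and the same implant, so losing both together may be the likelier pattern. There the gain is small. This also stands. Likewise, an unstable signal is not the same as an absent recording, so the stability hypothesis makes missing data plausible but does not establish a rate.

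Third, the mixed model is no better than the ANOVA on type I error if the DBS effect drifts differently between subjects. That is correct, and it is why the per-subject test belongs in the report.

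Two stronger readings are not supported. A reader might suppose that a lost recording can never be repeated; the documents are silent on this. A reader might also see an error in hypothesis 2, which expects that "We expect that in PD, DBS-induced changes will appear in early recordings" while in dystonia "changes will be seen only after long-term DBS". Here DBS-induced could mean on versus off at one visit, or change from before stimulation, as the PAC analysis defines it. Since one goal is to "Study acute and chronic effects of therapeutic DBS on" cortical activity, the meaning is worth stating in advance, but that is a secondary clarification.

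**Conclusion.** The point holds as a cheap improvement. If the ANOVA is run in its classical form, subjects with any missing cell are lost. With three time points, the standard error of the between-disease early-to-12-month contrast rises by about 2–6% (5% missing) or 3–13% (10%) when whole visits are lost or recording stops, and by about 13–15% or 25–29% when single recordings are lost independently. With complete data the two approaches give the same estimate, so no precision is lost by changing.

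The missing rates, patterns, time points and variance structures are all assumed. It would be wrong to conclude that the planned analysis is invalid or that a stated figure fails: the study claims no power, and this contrast is imprecise even with every recording in hand.

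**What to change.** Replace the classical ANOVA with a linear mixed model:

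- **Data:** all available recordings made after stimulation therapy starts, on or off DBS, with a separate fit for each behavioural condition (rest, reaching task, walking).
- **Fixed effects:** disease, time, DBS state and their interactions.
- **Random effects:** subject, subject-by-visit and subject-by-DBS.
- **Degrees of freedom:** Satterthwaite or Kenward–Roger.
- **Pre-stimulation recording:** keep it out of the full factorial. Where it is needed, code disease, visit and state as one cell-mean factor over the observed cells and form the contrasts from that. A subject without the pre-stimulation value then keeps the other recordings.
- **Check:** report the per-subject contrast t test alongside (13 df with complete data). It needs only the recordings that enter the contrast, and it keeps type I error under subject-specific drift.
- **Reporting:** estimates with 95% CIs, labelled hypothesis-generating.

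Separately, state in advance which meaning of DBS-induced applies to the timing expectation in hypothesis 2.

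The cost is analysis-plan wording and standard software, with no new data. The downsides are a slightly more complex model, a small gain if few recordings or only whole visits are missing, no protection if loss depends on unobserved outcome, and power that stays low (39% at 1.0 SD with complete data).
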